Protocol: Peripheral Nerve Stimulation for Shoulder Pain: Dose Response

ID: IRB16-00510

NCT02928055

Document Date: 12/18/2020

8.0 Methods and Procedures I:

8.1 Will this research involve the following Social-Behavioral Procedures:

Check all that apply.

Name _____
 Psychological Testing _____
 Surveys/Questionnaires _____

8.2 Will this research involved any of the following Medical Procedures/Considerations:

Check all that apply.

Name _____
 Collection of Biohazardous Substances _____
 Study of Human Biological Materials (i.e. Urine Collection) _____
 Investigation/Approved Devices _____
 Study of Existing Data _____
 Medical Tests, Comparisons, Evaluations _____
 Clinical Assessments (EEG, EKG, SCID, etc.) _____
 Venipuncture (Blood Draw) _____
 Use of investigational devices _____
 Psychological testing _____

8.3 Identify Data Collection types for this study:

Check all that apply.

Name _____
 Audio-Recording/Video-Recording/Photographs _____
 Chart Review - Prospective _____
 Existing/Retrospective Data/Specimens _____
 Interviews, questionnaires or psychological tests _____

Note if you are doing, recordings, Video-Recording/Photographs then subjects will need to sign the MetroHealth Audio-Video Consent form. See the IRB Forms and Templates.

View: 08-01 Methods and Procedures II

8.1 Methods and Procedures II:

8.4 * Please specify in detail the methods and procedures that are involved in this research:

If this field is not completed your protocol will not be reviewed. Do not enter N/A. Please describe what methods and procedures will be involved in this research.

Study Summary: This is a pilot RCT to explore the role of muscle contraction as a mechanism produced by peripheral nerve stimulation (PNS) to reduce hemiplegic shoulder pain (HSP). Thirty subjects will enroll and receive a 3-week course of percutaneous IM PNS at one of 3 doses. Subjects will be randomized to receive the standard IM PNS treatment (15,120 total contractions), IM PNS at half the standard dose (7,560 total contractions), or IM PNS at 1.5 times the standard dose (22,680 total contractions). Dose will be controlled by differing the stimulation time per day (3h, 6h, or 9h) while keeping constant the duty cycle of stimulation. Subjects will be followed for 12 weeks after treatment.

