Outcomes Assessment: The primary outcome measure is the worst pain in the prior 7-days (BPI SF-3). Secondary measures include pain interference with ADLs (BPI SF-9); QoL (SF-36); shoulder impairment (isometric voluntary abduction shoulder torque (IVAST), shoulder kinematic analysis, optional Fugl-Meyer Motor Assessment (upper limb)); and measures of central sensitization (mechanical pain thresholds for hyperalgesia, optional pinprick pain thresholds for hyperalgesia, temporal summation of repetitive pin-prick stimuli). Other optional measures include tactile/touch, vibration and thermal/thermal pain detection thresholds, temporal summation of repetitive thermal stimuli, and Conditioned Pain Modulation (CPM). Details for each measure are presented below. The outcomes are administered face-to-face in a blinded manner.

Brief Pain Inventory SF-3: The BPI has excellent psychometrics [86-92] and is recommended by the IMMPACT group for the assessment of pain in clinical trials. [75] The developers of the BPI recommend BPI SF-3, the "pain worst" rating, as the primary response metric. The question asks participants to rate their worst pain in the prior 7-d on a 0 to 10 NRS, where "0" indicates "No pain" and "10" indicates

“Pain as bad as you can imagine.” In order to gain a more comprehensive assessment of participants’ pain experience, daily least pain (BPI SF-4), daily average pain (BPI SF-5) and daily present pain (BPI SF-6) after morning ADLs are also collected. To analyze successful treatment, short-term responders will be defined as those who have a clinically meaningful 30% reduction of pain [72] at end of treatment. Long-term responders will be those who continue to have 30% reduction at weeks 8 and 12. The investigative team has extensive experience with the BPI. [2, 5, 8, 10, 11, 13, 70, 71, 93, 94]

Pain interference with ADLs – BPI SF-9: BPI SF-9 specifically evaluates the impact of pain on ADL performance within 7 domains of daily activity over a 7-day period: general activity, mood, walking ability, normal work, relations with other people, sleep and enjoyment of life on a 0-10 NRS, where 0 indicates “does not interfere” and 10 indicates “completely interferes.” [124] The BPI SF-9 score is the average of the scores for the 7 domains. Psychometrics have been evaluated as part of the BPI battery. [86-89] BPI SF-9 has been used to evaluate the impact of percutaneous PNS mediated pain reduction on ADLs. [6, 8, 11, 13, 62, 70]

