Visit 6 - EOT Outcomes Assessment & Explant Procedure: Study outcome measures administered (4 weeks post-Implant). PGIC administered. Skin checked, subject queried for medication usage and adverse events. Lead Removed. X-rays performed (may be done as separate clinical visit). (~4.5 hrs)

Phone Call #3 - 1 week Post-Explant Safety Check: Subject queried on condition of Lead exit site. (15 min)

Visit 7 - 8-wk Outcomes Assessment: Subset of study outcome measures

(questionnaires only) administered (8 weeks post-Implant (4 weeks post-EOT)).
Subject queried for medication usage. (~1 hr)

Visit 8 - 12-wk Outcomes Assessment: Subset of study outcome measures
(questionnaires only) administered (12 weeks post-Implant (8 weeks post-EOT)).
Subject queried for medication usage. (~1 hr)

Visit 9 - 16-wk Outcomes Assessment: Study outcome measures administered (16
weeks post-Implant (12 weeks post-EOT)). Subject queried for medication usage.
(~4 hrs)

Provision for lead replacement: If, in the judgement of the Investigator, the Sprint
MicroLead becomes significantly displaced or fully dislodged, it is possible that the
Investigator may elect to place another lead which would require an unscheduled
visit and additional 48-72 hour safety check. Other visits may be repeated as
appropriate.

Unscheduled Visits are conducted if/as needed.

8.7 Please attach study design/subject visit schedule here:

Name	Description
PNS Dose for HSP Visit Schedule Table (06-14-2017) History	

*If you have an
electronic schedule of study visits
and/or procedures please attach
here.*

View: 09-00 Inclusion/Exclusion Criteria

9.0 Inclusion/Exclusion Criteria:

9.1 What are the inclusion criteria? Put this information in bullet form:

- shoulder pain localized to the glenohumeral joint, subacromial area or deltoid insertion associated with: a) rest; b) passive abduction or external rotation range of motion (ROM); c) active abduction ROM; or, d) manual palpation;
- shoulder pain onset or worsening after the most recent stroke;
- weakness of shoulder abductors ($\leq 4/5$ on MRC if isolated movement is present);
- ≥ 21 -yrs old; < 90 -yrs old;
- time of stroke ≥ 3 -mo;
- duration of HSP ≥ 3 -mo;
- HSP with moderate to severe pain (BPI SF-3 ≥ 4);
- cognitive and communication ability to fulfill study requirements (cognitive ability based upon a score of ≥ 24 on the Mini Mental Status Exam (MMSE));
- availability of reliable adult who can assist with study procedures if necessary;

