Yu, [name] and associates, including current SPR and NDI staff, then went on to enroll 61 subjects into a multi-center single-blinded randomized controlled study to assess the safety and effectiveness of percutaneous electrical stimulation for post-stroke shoulder pain. To qualify for participation in the study, subjects had to be more than 12 weeks post stroke and rate their shoulder pain as at least a 2 on the pain intensity question of the Brief Pain Inventory, which is an 11-point numeric rating scale that asks subjects to rate their worst shoulder pain in the last week. Treatment subjects had four percutaneous leads placed in the posterior deltoid, middle deltoid, supraspinatus, and upper trapezius muscles. They were instructed to keep stimulation ON for a total of 6 hours a day during the 6-week treatment period. Control subjects were given a cuff type sling to use whenever the hemiplegic arm was unsupported during the 6-week treatment period and permitted to continue other pain therapies such as PT, OT, and medications.

Subjects were assessed at baseline, at 3-weeks, at EOT, and at 3-, 6-, and 12-months post-EOT. The primary outcome measure was the same as in the present study (BPI pain intensity). However, these data were collected on the BPI form rather than a subject diary. Secondary measures included the same Pain Interference Question of the BPI (BPI 9) as is planned for use in the present study and a variety of physical functioning assessments, including pain-free passive external rotation range of motion (ROM) of the glenohumeral joint.

The group receiving electrical stimulation demonstrated a significantly higher success rate (as measured by a minimum 2-point reduction on the scale) than the control group (84% vs. 31%, $p=.001$ at the end of treatment; and 63% vs. 21%, $p=.001$ for all follow-up visits). In addition, 34% (11 subjects) of the group receiving electrical stimulation were pain free (reported "0", indicating no pain) at the EOT compared to only 3.4% (one subject) in the control group.

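### Is the long-term responder rule unusable because its weeks 8 and 12 have no stated starting point?

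*Protocol*

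**What the plan says.** In section 8.4, under Outcomes Assessment, the BPI SF-3 paragraph first defines a short-term responder by a 30% fall in pain at end of treatment. It then adds: "Long-term responders will be those who continue to have 30% reduction at weeks 8 and 12". No time origin is attached to the two week numbers.

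Section 8.6 gives the visit calendar:

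- Visit 6 is the EOT assessment: "Study outcome measures administered (4 weeks post-Implant".
- Visit 7, titled as the 8-week assessment: "questionnaires only) administered (8 weeks post-Implant (4 weeks post-EOT".
- Visit 8, titled as the 12-week assessment: "questionnaires only) administered (12 weeks post-Implant (8 weeks post-EOT".
- Visit 9, titled as the 16-week assessment, is dated 16 "weeks post-Implant (12 weeks post-EOT)). Subject queried for medication usage".

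The Study Summary at the start of section 8.4 counts follow-up from treatment: "Subjects will be followed for 12 weeks after treatment".

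**The concern.** The numbers 8 and 12 appear on both clocks of section 8.6 but at different visits, so the rule can be read in two ways that share only Visit 8.

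On the implant clock the category ends 8 weeks after EOT, and the last pain assessment plays no part in a category called long-term. On the EOT clock it runs to the last visit but skips Visit 7, so someone who lost response there and regained it would still count as having continued.

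The practical difference is a participant who is still responding 8 weeks after EOT and relapses by 12 weeks. That person is a long-term responder on the first reading and not on the second. With 30 participants in three arms, about 10 each, one change of class moves an arm's rate by 10 points. If the choice were left open until the data were in, it could also be made with the results in view.

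**Working it through.** **Calendar.** Section 8.4 gives one week of lead stabilization and a three-week course, so EOT falls at 1 + 3 = 4 weeks post-implant, as section 8.6 states for Visit 6. Weeks post-EOT are therefore weeks post-implant minus 4, and weeks from start of stimulation are weeks post-implant minus 1.

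| Visit | Post-implant | Post-EOT, computed | Post-EOT, stated | From start of stimulation |
|---|---|---|---|---|
| 6 | 4 | 0 | EOT | 3 |
| 7 | 8 | 4 | 4 | 7 |
| 8 | 12 | 8 | 8 | 11 |
| 9 | 16 | 12 | 12 | 15 |

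The stated times reproduce exactly. Weeks 8 and 12 select Visits 7 and 8 on the implant clock and Visits 8 and 9 on the EOT clock. No visit falls at week 8 or 12 from start of stimulation, so only two readings exist.

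**Which reading the text favours.**

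- For Visits 7 and 8: the visit titles use the implant clock and match the rule's two numbers; the post-EOT times appear only in nested brackets. Continuing response is also naturally judged at the first two assessments after EOT.
- For Visits 8 and 9: the preceding sentence is anchored to EOT, and the Study Summary counts 12 weeks of follow-up from treatment. That statement gives the length of follow-up, however, and does not number the visits.

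The two readings are not evenly balanced. The visit names favour Visits 7 and 8.

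**Size, under assumptions.** The only anchor is the earlier randomized trial in section 21.21. It reports 84% success at EOT in the stimulation arm and, against its control, "63% vs. 21%, $p=.001$ for all follow-up visits". Its schedule was: "Subjects were assessed at baseline, at 3-weeks, at EOT, and at 3-, 6-, and 12-months post-EOT". It used a 2-point criterion, four leads and six weeks of treatment, so it is a rough guide only. Assume that response once lost is not regained, and that a constant fraction r is kept per 4 weeks. The rate is then 0.84 × r² for Visits 7 and 8 and 0.84 × r³ for Visits 8 and 9.

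- Loss spread over 52 weeks (13 periods): r = (0.63/0.84)^(1/13) = 0.978. The rates are 80.4% and 78.6%, a gap of 1.8 points. Expected changes of class: 30 × 0.0176 = 0.5. Chance of at least one: 1 − (1 − 0.0176)^30 = 41%.
- All of that loss within 12 weeks (3 periods): r = 0.75^(1/3) = 0.909. The rates are 69.3% and 63.0%, a gap of 6.3 points. Expected changes: 30 × 0.063 = 1.9.

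With freely assumed inputs (EOT response p from 50% to 84%, kept fraction k from 70% to 95% per 4 weeks), the gap p·k² − p·k³ = p·k²(1 − k) runs from 0.50 × 0.9025 × 0.05 = 2.3 points to 0.84 × 0.49 × 0.30 = 12.3 points. A simulation that allows response to be regained, with per-visit rates of 50% to 84% and correlations of 0.6 or 0.8, gave gaps of 0 to 11.5 points.

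**The case for a change.** The strongest case for a change is that the protocol itself sets this rule as its test of successful treatment and sets it loosely, so it is not a detail simply left to an analysis plan. Both readings have support in the text and each has an awkward consequence. The sentence naming the primary outcome gives no assessment visit, so the two responder rules are the only timed pain criteria in the text shown. Naming the visits would cost a few words and no new data.

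Part of this stands. The origin is missing, the EOT reading remains possible, and visit numbers would be tidier. Three things limit it.

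- The visit titles supply a ready default, so an analyst is not choosing blind.
- Ending the category 8 weeks after EOT is a legitimate design choice. Nothing in the protocol says that long-term must mean the last visit, and preferring Visits 8 and 9 is a view about how much durability to ask for.
- Sections 8.7 and 10.4 refer to an attached visit schedule and an attached outcomes and analysis document. Neither is shown, and either may settle the point.

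The 10-point movement per participant holds for any binary outcome with about 10 per arm and does not measure this gap. Whichever reading is used applies to all three arms, so no bias between doses has been shown.

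**Conclusion.** No change to the plan follows. This is missing detail that the protocol's own visit names fill sensibly: weeks 8 and 12 are most naturally Visits 7 and 8, and the resulting category is sound for what it measures, namely response held to 8 weeks after EOT. It supplements the primary outcome and does not bear on the sample size or on trial conduct. BPI pain is scheduled at Visits 6 to 9, so the other version can be computed and reported from the same data if anyone wants it.

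The effect on the responder rate cannot be derived from the documents. The one available anchor gives about 0.5 of 30 participants changing class if loss is spread over a year, and about 1.9 of 30 if it all comes in the first 12 weeks. Both figures assume steady loss without regain and borrow rates from a trial with a different criterion and treatment. Larger gaps, up to about 12 points, arise only with freely assumed rates.

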The perceived magnitude of a single pinprick stimulus will be compared with that of a train of 10 pinprick stimuli of the same force (256mN OR 512mN) repeated at 1/s rate at the same sites. The use of the larger stimuli will be made if, when presented at the first test site, the perceived pain rating is "0" for the lesser of the two. Thus, a greater differentiation of response may be possible, but will not present a significant discomfort to the subject. In all tests, the subject can stop the testing procedures. Single pinprick stimuli will be alternated with a train of 10 stimuli until both are done at three different sites: affected shoulder, unaffected shoulder, and unaffected tibialis anterior (lower leg). The mean pain rating of trains divided by the mean pain rating to single stimuli will be calculated as wind-up ratio (WUR). [116]

Several other outcomes measures also will be optional and may not be completed if the testing is found to take an excessive amount of time or if the subject is, for any reason, unable or unwilling to complete all of the testing. These include:

Tactile/touch detection thresholds will be measured using stimulus presentations of graded TouchTest von Frey monofilaments (North Coast Medical) at each test site. Using the ascending method of limits, the lowest force monofilament will be presented to the subject who will respond as to whether or not he/she felt the stimulus presentation, and increasing forces will be presented until the subject responds that he/she felt the stimulus. The second series of stimulus presentations will use the descending method of limits in which a stimulus force that is above threshold level will be presented and decreasing levels of force will continue to be presented until the subject indicates that he/she can no longer feel the stimulus. A second ascending and then a second descending series of stimulus presentations will occur, so that four estimates of threshold will be obtained at each site.

Vibration detection thresholds will be measured using the VSA 3000 Vibratory Sensory Analyzer component of a TSA-II Neurosensory Analyzer (Medoc, LTD; cleared commercially under K922052). The flat probe tip (1.22 sq cm) of the vibratory device will be held lightly against the skin, and the amplitude of the (100Hz) vibration will slowly increase until the subject reports that he/she can feel the vibration. Three trials will be performed at each test site.

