8.5 Does this study only involve the use of existing/retrospective data/specimens?

Check yes or no.

No

8.6 Describe in detail the study design also known as the experimental flow. Include all study procedures a subject will go through, in order of sequence and timing, including frequency of visits, duration of visits, length of subject participation etc. Please Note this needs to be written for an educated person who is not an expert in the field, do not exceed 300 words:

This is also known as NIH Experimental Procedure section or Clinical Trial Procedure/Experimental Flow section. Do not just attach documents in response to this question you must do a study design summary for IRB Review.

The duration of each subject's participation will be ~4 months.

Visit 1 – Consent/Eligibility: Consent form signed; assessed for eligibility per inclusion/exclusion criteria; MMSE administered; BDI, PCS & FABQ administered; medical history, demographics, comorbidities, and medication use recorded; blood drawn for INR (in applicable subjects); pregnancy test (in applicable subjects). (~3.5 hrs)

Visit 2 – Baseline Outcomes Assessment: Study outcome measures (see Outcomes Assessment) administered to establish baseline levels. (~4 hrs)

Visit 3 - Sprint MicroLead (Electrode) Implant Procedure: Testing of muscle response with Sprint Test Needles; Implantation of percutaneous Sprint MicroLead. Subject given instructions on care of Lead exit site. Skin checked, subject queried for medication usage. Randomization to treatment group. Subset of study outcome measures (questionnaires only) administered. (~2.5 hrs)

Visit 4 - 48-72 hour Post-Implant Safety Check: Check the Lead exit site within 48-72 hours of the Implant procedure; dressing changed. (~1 hr)

Visit 5 - Start of Stimulation: Collection of parameter data; programming of external stimulator (Sprint Stimulator). Subject given instructions on use of System and care of Lead exit site. Skin checked, dressing changed, subject queried for medication usage and adverse events. Subset of study outcome measures (BPI-SF only) administered. (~2 hrs)

Phone Call #1 – One week after starting stimulation, subject queried on condition of Lead exit site, pain, adverse events. (30 min)

Phone Call #2 – Two weeks after starting stimulation, subject queried on condition of Lead exit site, pain, adverse events. (30 min)

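### Does the pinprick force rule need to say whether the 256 or 512 mN choice is kept or made again at Visits 6 and 9?

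*Protocol*

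**What the plan says.** Protocol section 8.4 (Outcomes Assessment) lists temporal summation of pin-prick stimuli among the secondary measures of central sensitization. The rating of one pinprick is set against the rating given to "a train of 10 pinprick stimuli of the same force (256mN OR 512mN) repeated at 1/s rate at the same sites". The step up in force is governed by one sentence: "The use of the larger stimuli will be made if, when presented at the first test site, the perceived pain rating is" zero for the lesser force. The stated reason is to allow better differentiation of responses without significant discomfort. Three sites are tested: affected shoulder, unaffected shoulder and unaffected tibialis anterior. The derived measure is a ratio: "The mean pain rating of trains divided by the mean pain rating to single stimuli will be calculated as wind-up ratio (WUR").

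Section 8.6 gives the schedule. At Visit 2: "Study outcome measures (see Outcomes Assessment) administered to establish baseline levels". At Visit 6: "Study outcome measures administered (4 weeks post-Implant"). At Visit 9: "16-wk Outcomes Assessment: Study outcome measures administered". Visits 3, 7 and 8 carry questionnaires only and Visit 5 the BPI-SF only, so pinprick testing falls at three visits. The force rule names no visit.

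**The concern.** WUR is of interest mainly as a change from Visit 2 to Visits 6 and 9. Section 8.4 requires the same force for the single stimulus and the train within a session, but says nothing about the same force across sessions. If the rule is applied afresh, a participant whose rating of 256 mN moves to or from zero is tested with a different stimulus at follow-up. A change in WUR would then mix a change of stimulus with a change in sensitization. The choice also rests on one site, so a changed rating there alters the stimulus at the other two even if they have not changed. If the force were not recorded, no later analysis could separate the two kinds of change. In a study of mechanism, that could blur one of the few measures of central sensitization that is not marked optional.

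**Working it through.** **What the text settles.** The force rule sits inside the description of how the test is performed: present 256 mN at the first site, and step up if it is rated zero. Section 8.6 then calls for the outcome measures at Visits 2, 6 and 9. Nothing in section 8.4 ties the rule to baseline or speaks of carrying a force forward. Read plainly, it is a per-session rule. Holding the Visit 2 force is a possible alternative, but a reader has to add it.

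**Does the choice of reading matter?** The documents give no pinprick ratings, standard deviations or effect of force, so any size rests on assumption. Inputs assumed:

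- Mean single rating at 256 mN of 1, 2 or 3; 512 mN adds 1 or 2 points.
- Between-person SD 1.5, within-person SD 1; whole-number ratings from 0 to 10.
- Train rating equal to single + 1.5 (additive) or single × 1.6 (proportional), before rounding.
- Force set by the 256 mN rating at site 1; WUR pooled over the three sites; summation itself unchanged.
- 200,000 or more simulated participants per scenario; ten per arm, which assumes an equal split of 30.

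*How often the force would change if re-chosen.* With no true change, 9-25%: 0.09 × 30 = 2.7 to 0.25 × 30 = 7.5 people. With a 1-point fall at all sites, 17-31%: 0.17 × 30 = 5.1 to 0.31 × 30 = 9.3 people.

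*Spurious median change in WUR:*

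| Scenario | Re-chosen | Held |
|---|---|---|
| No true change, either train model | 0 | 0 |
| 1-point fall at all sites, additive | about +0.14 to +0.33 | about +0.18 to +0.40 |
| 1-point fall at all sites, proportional | 0 | 0 |

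Repeat runs move the ends of these ranges by 0.01 to 0.02. The drift in the middle row has little to do with switching: a fixed increment divided by a smaller single rating gives a larger ratio. Holding the force does not remove it.

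*Largest gap between readings.* At mean rating 1, with 512 mN adding 2 and a 1-point fall, the medians are 0.20 re-chosen and 0.37 held, a gap of 0.17. The SD of the WUR change there is 1.25, so the standard error of a difference between two arms is 1.25 × √(2/10) = 0.56.

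*Only the first site changes.* With a fall of 1 or 2 points at site 1 alone and an additive train, the mean WUR change at the other two sites is -0.05 to -0.17 or -0.11 to -0.30 if the force is re-chosen, and 0 if held. The SD in the worst case is 0.946, giving a standard error of 0.946 × √(2/10) = 0.42, above 0.30. With a proportional train the shift is about 0 under both readings.

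*One unchanged site, by hand.* At 256 mN: single 2, train 3.5, WUR 3.5/2 = 1.75. At 512 mN with single 3: an additive train of 4.5 gives 4.5/3 = 1.50, a change of -0.25; a proportional train of 5.25 gives 5.25/3 = 1.75, no change.

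*Undefined ratios.* WUR cannot be computed when the mean single rating is zero. With a 1-point fall and an additive train, follow-up WUR is undefined in about 0.4-21% if the force is re-chosen and 4-30% if held. Holding is worse in all six of those scenarios. Avoiding zero ratings is what the step to 512 mN is for.

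**The case for a change.** The strongest case for acting is that this is an instruction to the assessor, not something an analysis plan can repair later. Section 8.4 fixes the procedure in detail and stops one step short; two assessors could apply the sentence differently, and an unrecorded force cannot be recovered. The choice also affects how many participants have a usable ratio. A further point is that a shift common to the arms cancels in the dose comparison only if sensitivity changes alike in every arm; under a true dose response it need not cancel fully.

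The silence stands, and so does the point that the force used ought to be on record. What does not stand is the step from silence to a fault. Whether the force is recorded cannot be judged here: section 14.7 lists assessment case report forms, and section 10.4 an attachment on outcome measures and data analysis, none of which is shown. Holding the force is better only when the first site alone changes and the train is additive, and that effect is within one standard error. On drift from a general fall in sensitivity, and on undefined ratios, applying the rule at each session does at least as well. A comparison limited to participants tested at one force would select on a rating made after randomization, and belongs in an analysis plan in any case.

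**Conclusion.** No change to the plan is needed. The protocol leaves one procedural step unstated, but its wording has a natural reading, the same rule covers all three arms, and that reading serves the rule's stated purpose. On assumed inputs, the two readings differ by at most 0.17 in group median WUR change and 0.30 in the mean at the other sites. Both are below one standard error of a two-arm difference (0.56 and 0.42), in a 30-person pilot where this is one secondary measure. Neither reading is better throughout, so there is no superior rule to substitute. The sizes depend entirely on the assumed ratings, SDs and train model. The reading of the text does not, though it could be overtaken by the case report forms or the outcomes attachment.

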Thermal detection and thermal pain function measures will be performed also using the TSA-II Neurosensory Analyzer. Thermal stimuli will be delivered via a thermal probe with contact area between 2.5 sq cm and 9 sq cm. The probe will be held lightly against the skin as the temperature increases (for warm detection and hot pain thresholds) or decreases (for cool detection and cold pain thresholds) from a baseline temperature that approximately matches the neutral skin surface temperature (32°C). Subjects will be instructed to verbally respond when the desired sensation is reached. (For example, during cool detection threshold trials, subjects will be instructed that the temperature will slowly change from a neutral temperature, and that they should tell us as soon as they detect any change in temperature at the test site. For cold pain threshold trials, subjects will be told that the temperature will slowly change from a neutral temperature, and that they should tell us as soon as they feel the sensation increase to a level that they would call painful.) Each type of sensation threshold (cool detection, warm detection, cold pain, hot pain) will be measured three times at each test site.

Temporal Summation of repetitive thermal stimuli will be assessed using the TSA-II Neurosensory Analyzer in a way comparable to Temporal Summation of repetitive pin-prick stimuli described earlier. The perceived magnitude of a single thermal stimulus will be compared with that of a train of 10 thermal stimuli of the same magnitude repeated at a 1/s rate at the same sites. The mean pain rating of trains divided by the mean pain rating of single stimuli will be calculated as wind-up ratio (WUR).

Conditioned Pain Modulation (CPM) is measured using a diffuse noxious inhibitory control (DNIC) protocol and analyzed through established methods. [121] The "test-stimulus" is a 7-sec presentation of a thermal noxious stimulus (between 43-49°C) to the volar forearm of the nonparetic limb, and the "conditioning stimulus" is the

immersion of the nonparetic foot/distal leg into a cold-water bath (12°C) for 60 sec. Pain intensity ratings of the test stimulus occur prior to the conditioning stimulus ("baseline" pain rating), and 40 sec after the conditioning stimulus is initiated ("conditioned" pain rating). The extent of CPM is calculated by subtracting the conditioned pain rating from the baseline pain rating of the test stimulus. [121]

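### The pinprick wind-up ratio can be undefined when a single stimulus is rated 0, because the only safeguard acts at the first test site; the train-minus-single difference should be reported with it

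*Protocol*

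**What the plan says.** Protocol section 8.4, Outcomes Assessment, lists among the secondary outcomes "measures of central sensitization (mechanical pain thresholds for hyperalgesia, optional pinprick pain thresholds for hyperalgesia, temporal summation of repetitive pin-prick stimuli"). The pinprick threshold is marked optional there; pinprick temporal summation is not.

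The later paragraph of 8.4 on repeated pinprick stimuli compares one stimulus with "a train of 10 pinprick stimuli of the same force (256mN OR 512mN) repeated at 1/s rate at the same sites". The choice of force depends on the response: "The use of the larger stimuli will be made if, when presented at the first test site, the perceived pain rating is '0' for the" lower of the two forces. The sequence is described as "Single pinprick stimuli will be alternated with a train of 10 stimuli until both are done at three different sites", namely the affected shoulder, the unaffected shoulder and the unaffected lower leg. The only parameter defined is "The mean pain rating of trains divided by the mean pain rating to single stimuli will be calculated as wind-up ratio (WUR").

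The optional thermal test in 8.4 uses the same form: "The mean pain rating of trains divided by the mean pain rating of single stimuli will be calculated as wind-up ratio (WUR"). It has no step to a stronger stimulus. Conditioned pain modulation (CPM), also in 8.4, is instead calculated by subtracting one rating from another.

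**The concern.** The denominator of the wind-up ratio (WUR) is a pain rating that the protocol itself expects may be 0. The force switch responds to a 0 at the first test site only. A participant who rates above 0 there stays at 256 mN and may still rate 0 at the second or third site. A participant moved to 512 mN may still rate 0, and no higher force is available. In either case a per-site WUR has no value, and the protocol states no rule for that.

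The direction of the problem matters more than the occasional lost value. If stimulation reduces pinprick pain, single-stimulus ratings move towards 0 after treatment, and the ratio is then lost or inflated in the participants who improved. The trial has 30 participants in three dose groups. By section 8.6 the full assessment takes place only at Visits 2, 6 and 9, so each lost value carries weight.

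**Working it through.** The protocol gives no figure to reproduce here and no frequency of zero ratings. All rates below are assumptions, shown over a range.

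**Algebra.** WUR = train / single has no value at single = 0. The difference D = train − single always has one.

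| Single | Train | WUR | D |
|---|---|---|---|
| 0 | 0 | undefined | 0 |
| 0 | 2 | undefined | 2 |
| 0.5 | 2 | 4.0 | 1.5 |
| 1 | 2 | 2.0 | 1 |
| 2 | 4 | 2.0 | 2 |
| 1 | 3 | 3.0 | 2 |

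Rows 3 and 4 show the instability near 0: half a point in the denominator doubles the ratio. In the last two rows both ratings fall by one point, D is unchanged, and the WUR rises from 2 to 3.

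**How often it could be undefined.** Assume one single-stimulus rating per site, Poisson with mean m at the force used, and independent sites.
- Per-site WUR undefined: exp(−m).
- WUR pooled over three sites undefined (all three ratings 0): exp(−3m).

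| m | One site | Pooled over three sites |
|---|---|---|
| 0.5 | 61% | 22% |
| 1 | 37% | 5% |
| 2 | 14% | 0.25% |
| 3 | 5% | 0.01% |

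The model ignores the force switch, so the one-site column overstates the rate at the first site.

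**The same in counts.** Let p be the probability of a 0 at one site and visit. Expected undefined per-site WURs among 30 participants are 30p. The chance of at least one in a group of 10 (equal allocation assumed) is 1 − (1 − p)^10.

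| p | Expected of 30 | At least one of 10 |
|---|---|---|
| 2% | 0.6 | 18% |
| 5% | 1.5 | 40% |
| 10% | 3 | 65% |
| 20% | 6 | 89% |
| 30% | 9 | 97% |

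If the three sites are pooled, the rate is p³: 0.1% at p = 10% (0.03 of 30 participants) and 2.7% at p = 30% (0.8 of 30).

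**Direction under treatment.** Assume a rounded normal rating, with P(0) = Φ((0.5 − mean)/SD).

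| Fall in mean rating | Start: mean 2, SD 1.5 | Start: mean 3, SD 2 |
|---|---|---|
| 0 | 16% | 11% |
| 0.5 | 25% | 16% |
| 1.0 | 37% | 23% |
| 1.5 | 50% | 31% |

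Under both assumptions, lower pinprick pain makes an undefined WUR more frequent.

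**The case against.** The strongest objection is that this is a derivation matter for the analysis plan. The single and train ratings are collected either way. Section 10.4 points to an attachment on outcomes and data analysis, and section 14.7 lists assessment case report forms. Neither is shown, and either could hold a zero rule or a repeat count. That lowers the weight of the point. It does not remove it, because the protocol itself fixes the ratio as the only parameter, anticipates zeros and guards against them only in part.

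The document also contains mitigations. Section 9.2 excludes insensate skin, and two of the three sites are on the unaffected side. These reduce the frequency of zeros, but skin can have sensation and still register no pain from one pinprick.

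A reader might go further in four ways that the text does not support:
- **Most participants lose the measure.** Under the same Poisson model, at least one of three sites lacks a WUR with probability 1 − (1 − exp(−m))³, which is 94%, 75%, 35% and 14% for m = 0.5, 1, 2 and 3. That holds only for a per-site WUR, ignores the force switch, and leaves the other sites usable. At a 5% zero rate, one site's three-visit series is complete in 0.95³ = 86% of participants, and all nine site-visits in 0.95⁹ = 63%.
- **Only one pair is applied per site.** That is one reading of the sequence sentence. The formula speaks of means and gives no count, so the number of repeats is ambiguous rather than fixed at one.
- **The sites exist to separate local from remote sensitisation.** The protocol lists them without stating that purpose.
- **The ratio is the wrong scale.** In the 2/4 to 1/3 example relative summation rises while absolute summation is constant. The two scales differ, and preferring one is partly a matter of choice.

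**Conclusion.** The point holds as a gap in one secondary outcome definition. Following the stated formula can give an undefined or unstable value, the safeguard covers one site and one step, and the gap would widen if stimulation lowers pinprick pain.

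Its size cannot be fixed from the protocol. Over the assumed range of mean ratings it runs from 61% to 5% of assessments for a single site, and from about 22% to 0.01% for a WUR pooled over three sites. Which applies depends on a choice the text leaves open. The figures rest on a Poisson rating, one rating per site, independent sites and no allowance for the force switch. That missingness depends on response is a conditional inference, not a documented fact.

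It would be wrong to infer that the trial loses its reading of central sensitisation. Pressure pain thresholds are also non-optional and are unaffected, as is the primary outcome, BPI SF-3. The thermal ratio has the same weakness without any escalation rule, but that test is optional.

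**What to change.** For the pinprick test, and for the thermal test where done, derive from the ratings already collected the difference, train minus single, at each site. Report it and analyse it for all participants. It is defined at 0 and has the same subtractive form that the protocol uses for CPM. Keep the WUR alongside it where the single rating is above 0, report the number of undefined WURs by arm and visit, and state whether the WUR is per site or pooled.

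The cost is a change of wording and one more reported parameter, on a scale different from the conventional WUR. No added stimulus repeats, visits or participant burden are required. The difference does not remove the floor of the scale: a pair rated 0 and 0 gives a difference of 0, but the participant stays in the analysis.
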